## **Appendix A: Standardized perioperative anesthetic protocol**

### Preoperatively:

1. Tylenol 1000 mg po, Celebrex 200 mg po.
2. No gabapentin administration unless patient is chronically preoperatively receiving medication. In such a scenario, the patient would take their normal gabapentin dose the morning of surgery
3. Scopolamine patches for patients at high risk for postoperative nausea and vomiting, oral caffeine for headache prophylaxis in caffeine users, and midazolam for anxiolysis can be administered at the anesthesiologist's discretion.
4. For those patients who will receive an intrathecal opioid (150 mcg of hydromorphone), midazolam and fentanyl may be administered for procedural sedation.

### Intraoperatively:

1. The anesthetic will include induction with propofol and either succinylcholine or a non-depolarizing muscle relaxant. Maintenance will include volatile anesthetic/air/oxygen. A background propofol infusion may be administered for postoperative nausea and vomiting prophylaxis at the anesthesiologist's discretion.
2. No dexmedetomidine, lidocaine, ketamine or remifentanil infusions.
3. Intravenous fentanyl will be administered by the anesthesia team per the discretion of the anesthesiologist with a goal of no more than 500mcg fentanyl throughout the case.
4. Postoperative nausea prophylaxis with 8 mg of IV dexamethasone, 4 mg of ondansetron, 0.625 mg of droperidol, Ketamine 10 mg IV at the beginning and at the end of the case.
5. Ketorolac 15 mg IV may be given if stratified to "plan for NSAID use" at the anesthesiologist's discretion.

### Postoperatively in the PACU:

1. Fentanyl orders in the PACU: 25 mcg IV Q 2minutes prn pain 4 or greater up to 100 mcg maximum. If max dose of fentanyl is reached, discontinue fentanyl and give intravenous hydromorphone. Hydromorphone0.2 mg Q 5 minutes IV prn pain score 4-10 up to 2 mg maximum.
2. If maximum opioids are reached in the PACU, further opioid prescribing is per the discretion of the anesthesiologist.
3. Ketamine 10 mg IV may be given prn breakthrough pain at the anesthesiologist's discretion.
4. Rescue antiemetics, droperidol, Zofran, Kytril at the anesthesiologist's discretion.

5. Caffeine 250 mg IV will only be given at the anesthesiologist's discretion.
6. Ditropan: 5 mg po once as needed for bladder spasms
7. Demerol: 12.5 mg IV Q 15 min prn shivering up to 2 doses maximum.
8. Acetaminophen 1000 mg IV or po, if 6 or more hours have passed since the preoperative dose.
9. Ketorolac 15 mg IV may be given if stratified to "plan for NSAID use" at the anesthesiologist's discretion if it was not previously given in the OR.

#### **Appendix B. Postoperative pain Management**

1. Tylenol 1000mg po every 6 hours
2. Ketorolac 15 mg IV every 6 hours X 4 doses if stratified to "plan for NSAID use"
3. Ibuprofen every 6 hours if stratified to "plan for NSAID use", start 6 hours after the last Ketorolac dose. See table below for dose.

Ibuprofen dose	Weight <50 kg	Weight 50-80 kg	Weight >80 kg
Age <65	200	600	800 q 8 hours
Age >65	200	400	600

4. Oxycodone 5mg every 4 hours PRN for moderate pain or pain score of 4-6/10. Administer if pain is unrelieved by Tylenol. For patients who received intrathecal analgesia, start 24 hours after intrathecal dose was given.
5. Oxycodone 10mg every 4 hours PRN for severe pain or pain score of 7-10/10. Administer if pain is unrelieved by Tylenol. For patients that received intrathecal analgesia, start 24 hours after intrathecal dose was given.
6. Dilaudid 0.4mg IV every 2 hours PRN for breakthrough pain. To be given if pain is unrelieved 30 minutes after PRN oral medication is used; if unable to take oral pain meds; or if pain is greater than or equal to 7, use instead of oral pain medication.
7. Oral intake, timing of Foley catheter removal and ambulation in accordance to ERAS protocol and discretion of the surgeon.

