##### Exclusion:

1. Inability to read or understand English
2. Prehospitalization narcotic use if weekly average daily oral morphine equivalent of  $>20$  mg.
3. Chronic pain syndromes such as fibromyalgia.
4. Extensive surgery planned (surrogate for postop pain): Planned ICU admission, abdominoperineal resection, exenteration, use of IORT, HIPEC
5. Contraindication to neuraxial analgesia:
  - a. Coagulopathy
    - i. INR  $>1.2$  Current or predicted after surgery (e.g. planned right hepatic resection)
    - ii. Thrombocytopenia. plts  $<100$ .
    - iii. Hemophilic disease states (hemophilia, von Willebrand disease, etc.)

- iv. Patients receiving antithrombotic or thrombolytic therapy are excluded according to the ASRA guidelines (Reference:  
<https://rapm.bmjjournals.org/content/rapm/43/3/263.full.pdf>)
- b. Localized infection at the potential site of injection
- c. Significant developmental or structural spinal abnormalities that would preclude a safe spinal technique. These include spina bifida, tethered spinal cord, lumbar spinal fusion, and active lumbar radiculopathy.
- 6. Patients with stage 4 or 5 kidney disease (GFR less than 30 ml/min per 1.73 m^2).
- 7. Intolerance or allergy to opioids, acetaminophen, or amide-type local anesthetics
- 8. Current pregnancy

**Intervention:** ITA with 150mcg of hydromorphone in addition to ILB. For patients randomized to ITA, injection will be performed in the O.R.

**Comparator:** ILB

Standardized perioperative anesthetic protocol (Appendix A) and postoperative protocol (Appendix B) will be used

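### Appendix B items 4 to 6 give conflicting opioid orders at pain 7–10 and leave pain 4–6 not clearly covered during the oxycodone hold in the intrathecal arm

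*Combined protocol and SAP*

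**What the plan says.** Section C.2 adopts Appendix B as the postoperative protocol for the trial. Three of its items govern opioids given as needed.

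- **Item 4** orders oral oxycodone 5 mg for pain 4–6. It adds, for one group of patients only: "For patients who received intrathecal analgesia, start 24 hours after intrathecal dose was given".
- **Item 5** reads "Oxycodone 10mg every 4 hours PRN for severe pain or pain score of 7-10/10", with the same restriction: "For patients that received intrathecal analgesia, start 24 hours after intrathecal dose was given".
- **Item 6** orders IV Dilaudid for breakthrough pain. Two of its triggers are "To be given if pain is unrelieved 30 minutes after PRN oral medication is used; if unable to take oral pain meds". The third is "if pain is greater than or equal to 7, use instead of oral pain medication".

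The other analgesics in Appendix B (Tylenol, ketorolac, ibuprofen) are scheduled, not given as needed. The PACU orders in Appendix A do cover pain of 4 or more with IV opioids in both arms, for example "Hydromorphone0.2 mg Q 5 minutes IV prn pain score 4-10 up to 2 mg maximum", but only in the PACU.

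The hold is timed from the intrathecal dose, and Section C.2 says where that is given: "For patients randomized to ITA, injection will be performed in the O.R". The secondary outcomes in Section C.2 include 24 h opioid consumption in MME, use of IV rescue opioids, and pain scores at 4, 8, 16 and 24 h. Section C.1 states that there is no blinding. The statistical analysis plan does not mention that the opioid orders differ by arm.

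**The concern.** A standardized protocol should tell staff which order applies to a given patient at a given pain score. Items 4 to 6 fail to do so in two places. At pain 7–10, two items name different drugs and routes. At pain 4–6 during the hold, no item clearly applies.

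Patient care comes first: a nurse facing either situation has to interpret the orders. The statistical consequence follows from that. Staff know the allocation, and the orders open to them depend on it. Some of the between-arm difference in IV rescue, 24 h MME or pain scores during the hold may then come from the written orders, or from how they were read, in addition to the analgesic effect of the intrathecal drug.

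**Working it through.** The plan gives no figure on this point, so the check is mainly a reading of items 4 to 6 for each arm, period and pain band.

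**Step 1. Which order applies after the PACU**

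| Pain score | Comparator, throughout | ITA, during hold | ITA, after hold |
|---|---|---|---|
| 4–6, can take oral medication | Oral oxycodone (item 4) | No clearly applicable opioid order | Oral oxycodone (item 4) |
| 7–10 | Items 5 (oral) and 6 (IV) conflict | IV Dilaudid (item 6) only | Items 5 and 6 conflict |

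The 7–10 conflict is absent for ITA patients during the hold because item 5 is inactive for them. The 4–6 gap arises because item 6, below pain 7, needs either a prior as-needed oral dose or inability to take oral medication. Oxycodone is the only as-needed oral order in Appendix B, and it is the one withheld.

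**Step 2. What each reading implies during the hold**

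- Pain 7–10, item 6 governs: IV in both arms. Item 5 is then never the first order at any score.
- Pain 7–10, item 5 governs: comparator oral, ITA IV. The last clause of item 6 then has no effect while oxycodone is active.
- Pain 4–6, a withheld order counts as inability to take oral medication: comparator oral, ITA IV.
- Pain 4–6, it does not count: comparator oral, ITA has no applicable Appendix B opioid order.

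**Step 3. How long the hold lasts after surgery**

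Let h be the hours from intrathecal dose to end of surgery. The documents do not give h; assume 2–8 h. The hold ends 24 − h hours after surgery.

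- h = 2: 22 h, and 22/24 = 92% of the first 24 h.
- h = 8: 16 h, and 16/24 = 67%.

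Let s be the hours from end of surgery until a comparator patient could first receive oral oxycodone. It is not stated either: the PACU orders contain no oral oxycodone, and item 7 leaves it open ("Oral intake, timing of Foley catheter removal and ambulation in accordance to ERAS protocol and discretion of the surgeon"). Assume 1–6 h. Oral oxycodone availability then differs between arms for 24 − h − s hours.

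- Longest: 24 − 2 − 1 = 21 h (88%).
- Shortest: 24 − 8 − 6 = 10 h (42%).

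The 8 h pain score falls in this period for all these values. The 16 h score does so if h is below 8 h (at h = 8 the hold ends exactly then), and the 4 h score only if s is below 4 h. The 24 h score falls outside it.

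**Step 4. Whether a direction for MME follows**

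The ceilings over 24 h from the stated orders are:

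- item 5: 10 mg × 6 = 60 mg oral oxycodone;
- item 6: 0.4 mg × 12 = 4.8 mg IV Dilaudid.

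The documents give no conversion factors. The ceilings are equal if 1 mg IV Dilaudid counts as 60/4.8 = 12.5 mg oral oxycodone. Over an assumed factor of 5 to 25, the IV ceiling equals 4.8 × 5 = 24 mg to 4.8 × 25 = 120 mg, against 60 mg. The choice of order could therefore move MME either way, and no direction follows.

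**The case against.** The strongest reply is that the items can be harmonized. Item 6 is headed as a breakthrough order, so it could be second-line after items 4 and 5; or its final clause could set precedence at pain 7 or more. Either is workable, but the first leaves that final clause without effect while oxycodone is active, and the second leaves item 5 without a score at which it comes first. The text does not say which is meant. For pain 4–6, one can count a withheld drug as inability to take it, or treat scheduled Tylenol as the as-needed oral dose. Both stretch the wording.

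Other parts of the reply stand.

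- The hold is explicit, is stated twice, and is part of the randomized ITA strategy. It is not itself a defect.
- Appendix B does not appear to be a closed list. Patient-controlled analgesia is a secondary outcome but has no order there. A reader might infer that ITA patients with pain 4–6 are left without analgesia; the documents do not support that. Scheduled Tylenol continues, as does scheduled NSAID treatment where planned, and other opioid orders may exist.
- A reader might infer that the 7–10 conflict runs throughout in both arms. It does not, because item 5 is inactive for ITA patients during the hold.
- Opioid route is not a listed outcome; IV rescue use and MME are.

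**Conclusion.** Both inconsistencies are present in the text. The 7–10 conflict affects the comparator arm throughout and ITA patients only after the hold. The 4–6 gap affects ITA patients outside the PACU during the hold. As written, the standardized protocol cannot be followed consistently. That bears on patient care and may affect IV rescue use, 24 h MME and pain scores during the hold.

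The period in which oral oxycodone availability differs, 10–21 h, rests wholly on the assumed h and s. It is a length of exposure, and a reader should not take it as an effect on any outcome. At pain 7–10 the hold makes no difference to the route if item 6 governs. The direction and size for MME and IV rescue cannot be determined.

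Because OBAS includes pain and opioid side effects, a reader might also infer bias in the primary non-inferiority comparison. The documents do not support that: the hold belongs to the strategy being randomized, the comparison of strategies remains valid, and no direction can be shown.

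**What to change.** The sponsor should reconcile items 4, 5 and 6 of Appendix B with each other, so that they state which order applies at pain 7–10 in both arms and at pain 4–6 during the ITA hold. Which rule is right is a clinical decision, and none is proposed here.

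The statistical analysis plan should add one sentence saying that between-arm differences in IV rescue use and 24 h MME are interpreted as effects of the ITA strategy including its oral-opioid hold.

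The cost is the wording of three items and that sentence, with no added patients or visits. The price is a narrower claim for these secondary outcomes. Reporting 24 h MME by route (oral, IV) as well as in total is optional; it would add one table from opioid data already needed for MME and IV rescue.
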